4.2 Treatment Groups

The 2 treatment groups are zavegepant 10 mg and placebo. The safety analysis set is assessed by as-treated treatment group (i.e., actual treatment received), the randomized, full, efficacy, and outcomes research analysis sets are assessed by as-randomized treatment group, and the enrolled analysis set is assessed overall.

If a subject receives ≥ 1 dose of planned randomized study drug, then that subject is considered to have as-treated treatment group equal to as-randomized treatment group.

If there are non-randomized subjects who receive study drug, then the as-randomized treatment group of “not randomized” is included for the full analysis set.

4.3 Subgroups

For the efficacy analysis set, the following efficacy subgroups are of interest:

- **Age:** < 40 , ≥ 40 years
- **Sex:** female, male
- **Race:** White, Black or African American, Other including Asian, Asian
- **Ethnicity:** Hispanic or Latino, Not Hispanic or Latino

- Baseline body mass index (BMI; kg/m²): < 25, ≥ 25 to < 30, ≥ 30
- Aura on study before dosing: yes, no (see Section 6.2.5.2)
- Historical number of moderate or severe migraine attacks per month: < median, ≥ median, where the median is calculated overall across treatment groups combined for the efficacy analysis set and rounded to an integer (see Section 6.2.5.2)
- Triptan non-responder: yes, no (refer to the Zavegepant Core SAP)

Subgroup analyses are performed for the co-primary efficacy endpoints only. Efficacy subgroup tables present results by subgroup level for subjects with non-missing subgroup level data, unless specified otherwise.

Subgroup levels may be redefined or combined based on the availability of data.

5 SAMPLE SIZE, POWER, AND TYPE 1 ERROR

It is anticipated that about 90% of the 700 subjects randomized to each treatment group will have a headache in the allotted time period, resulting in approximately 630 subjects evaluable for efficacy in each treatment group.

The sample size calculation is based on results from the Phase 2/3 dose-ranging study BHV3500-201. The response rates for the pooled zavegepant 10 mg and 20 mg groups, and for the placebo group in study BHV3500-201 were 22.8% and 15.5%, respectively, for pain freedom at 2 hours postdose, and 42.2% and 33.7%, respectively, for MBS freedom at 2 hours postdose.

A total sample size of 1,260 evaluable subjects (630 per treatment group) provides approximately 91% power for the co-primary endpoint of pain freedom at 2 hours postdose, approximately 88% power for the co-primary endpoint of MBS freedom at 2 hours postdose, and approximately 80% power to detect a difference between treatment groups for both endpoints jointly.

Type I error is controlled by a hierarchical gate-keeping procedure. First, the family of 2 co-primary endpoints is tested. In particular, zavegepant is tested for superiority against placebo at an alpha=0.05 level for both co-primary endpoints. If the tests of both co-primary endpoints are significant (i.e., both p-values are ≤ 0.05), then the secondary endpoints are tested hierarchically at the alpha=0.05 level in the order shown in the Section 3.1.2, using the efficacy analysis set. Thus, a secondary endpoint is tested only if the preceding secondary endpoint in the hierarchy is determined to be significant (i.e., p-value ≤ 0.05). If a test in the hierarchy is not significant, then any further tests on endpoints in the sequence have p-values presented only for descriptive purposes, and no conclusions are drawn from those results.

For exploratory endpoints, no attempt is made to adjust for multiplicity. Any exploratory endpoints for which p-values are produced are evaluated at an unadjusted, 2-sided alpha=0.05 level and presented only for descriptive purposes.

6 STATISTICAL ANALYSES

All statistical analyses are performed using SAS statistical software (Version 9.4 or higher).

6.1 General

6.1.1 Programmed Output

A list of TLFs and corresponding templates are presented separately in a mock TLF document corresponding to this SAP.

Refer to the Zavegepant Core SAP for additional details about programmed output.

6.1.1.1 Tables

Treatment Group Presentation

Tables present results by treatment group (i.e., zavegepant 10 mg and placebo) with the following exceptions:

- Results for the enrolled analysis set are presented only by overall, without treatment group.
- Results for study population parameters (see Section 6.2) and pre-treatment safety also include overall.

Time-to-event Tables

Time-to-event endpoints are summarized with Kaplan-Meier tables. Refer to the Zavegepant Core SAP for additional details.

Time-to-event distributions of endpoints are tabulated with the following descriptive statistics: number and percentage of subjects with events; number and percentage of subjects censored in or before the last time interval; number and percentage of subjects censored in the last time interval; time-to-event median with 95% CI, first quartile, and third quartile. The 95% CI for the median is estimated using the method of Brookmeyer and Crowley.

6.1.1.2 Listings

Unless specified otherwise, by-subject listings are sorted by randomization status (randomized, not randomized), site-subject ID, and additional variables such as time points, as applicable. Listings display as-randomized treatment group.

All listings except administrative listings identify subjects who are impacted by COVID-19 (see Section 9.1.2).

Listings of non-study medications, safety parameters, and COVID-19 visit impact display both study day and treatment day (see Section 7.3). Other listings display study day only, if applicable.

Select listings display COVID-19 visit impact code for visits that are impacted by COVID-19 (see Section 9.1.5.2).

Refer to the Zavegepant Core SAP for additional details about listings.

6.1.2 Statistical Methods

Refer to the Zavegepant Core SAP for descriptive statistics in summary tables, counting rules in frequency tables, and rounding rules.

6.1.3 Missing Data

For all binary efficacy endpoints, main analyses impute missing data as failure using methods described in Section 6.3. Sensitivity analyses of the co-primary endpoints exclude subjects with missing data, or impute missing data using different methods (see Sections 6.3.2.1 and 6.3.2.2). Sensitivity analyses of exploratory efficacy endpoints exclude subjects with missing data (see Section 6.3.4.2). Otherwise, all analyses are based on observed data without using imputation.

6.2 Study Population

6.2.1 Analysis Sets

The number of subjects in each analysis set described in Section 4.1 is tabulated by treatment group (as-randomized for the randomized, full, and efficacy analysis sets; as-treated for the safety analysis set), not randomized, and overall.

Inclusion and exclusion from the efficacy analysis set is tabulated by treatment group and overall as the number and percentage of subjects in the full analysis set in the following categories:

- Included in the efficacy analysis set
- Excluded from the efficacy analysis set
 - Treated with study drug (i.e., study drug start date/time not missing)
 - Not randomized
 - Randomized more than once
 - Pain intensity of mild, none, or not reported at the time of dosing
 - No postdose efficacy data (i.e., missing all of the following parameters from the eDiary Postdose Migraine Report after the study drug start date/time: pain intensity, nausea status, phonophobia status, photophobia status, and functional disability level)
 - Not treated with study drug.

A by-subject listing of analysis sets is provided for the enrolled analysis set. Refer to the Zavegepant Core SAP for listing contents.

A by-subject listing of subjects excluded from the efficacy analysis is provided for the full analysis set. The listing includes the reason(s) for exclusion (e.g., not treated with study drug), as described previously.

An administrative listing of randomization scheme and codes is provided for all randomization numbers and block numbers, even those not assigned to a subject. Refer to the Zavegepant Core SAP for listing contents.

6.2.2 Enrollment

Enrollment by (1) country and site and (2) age group are tabulated for the enrolled analysis set. The enrollment by country and site table also displays results for the full and safety analysis sets. Refer to the Zavegepant Core SAP for additional details.

Accrual by randomization month and year is tabulated as the number and percentage of subjects in each time category defined by randomization month and year for the full analysis set. Study drug start month and year are used for non-randomized subjects who took study drug.

6.2.3 Subject Disposition

Subject disposition is based on the Study Exit Status CRF, unless noted otherwise. Note that the Study Exit Status CRF links non-completion due to AE to the AE CRF using numeric variables.

In tables, reasons for not completing a milestone are displayed in alphabetical order. The reason of “other” for not completing a milestone is displayed as “other” without the corresponding specify text.

A by-subject listing of subject disposition is provided for the enrolled analysis set based on the Study Exit Status CRF, and includes the following: study completion status (yes, no); reason for not completing the study, including specify text for “other” and AE preferred terms (PTs); IWRS randomization date; study drug start date/time; last contact date; and previous subject identifier from the Informed Consent/Demographic CRF. The listing also identifies subjects who terminated the study prematurely due to COVID-19 (see Section 9.1.4). See Section 7.1 for derived dates.

A by-subject listing of eligibility with inclusion and exclusion criteria is provided for all subjects in the enrolled analysis set, not just those who have non-missing criteria. This is based on the Inclusion/Exclusion Criteria CRF.

See Section 7.1 for derived dates.

6.2.3.1 *Subject Disposition from Enrollment to Randomization*

Subject disposition from enrollment to randomization is tabulated for the enrolled analysis set as the number and percentage of subjects in the following categories:

- Randomized
- Not randomized
 - Reasons for discontinuation (i.e., not completing the study), including not reported. For subjects whose reason is screen failure due to inclusion/exclusion criteria, the reasons for screen failure are also included from the Inclusion/Exclusion Criteria CRF.
- Not randomized and terminated the study prematurely due to COVID-19 (see Section 9.1.4)
 - Reasons for premature termination, including not reported. For subjects whose reason is screen failure due to inclusion/exclusion criteria, the reasons for screen failure are also be included from the Inclusion/Exclusion Criteria CRF.

6.2.3.2 *Subject Disposition from Randomization to Treatment*

Subject disposition from randomization to treatment is tabulated for the randomized analysis set by as-randomized treatment group and overall as the number and percentage of subjects in the following categories:

- Treated with study drug (identified as those with non-missing study drug start date).
- Not treated with study drug (identified as those with missing study drug start date)
 - Reasons for discontinuation (i.e., not completing the study), including not reported
- Not treated with study drug and terminated the study prematurely due to COVID-19 (see Section 9.1.4)
 - Reasons for premature termination, including not reported.

6.2.3.3 *Subject Disposition from Treatment to End of Study*

Subject disposition from treatment to end of study is tabulated for the safety analysis set by as-treated treatment group and overall as the number and percentage of subjects in the following categories:

- Completed the study (identified as those with “yes” response to the question “Did the subject complete the study?”)
- Did not complete the study (identified as those with “no” response to the question “Did the subject complete the study?”)
 - Reasons for not completing the study, including not reported
- Terminated the study prematurely due to COVID-19 (see Section 9.1.4)
 - Reasons for premature termination, including not reported.

Subject disposition is tabulated analogously for the efficacy analysis set by as-randomized treatment group and overall to support efficacy.

6.2.3.4 Overall Premature Study Termination due to COVID-19

Overall premature study termination due to COVID-19 is tabulated for the enrolled analysis set as the number and percentage of subjects in categories defined by reasons for premature termination, including not reported.

6.2.4 Protocol Deviations

6.2.4.1 Relevant Protocol Deviations

Relevant protocol deviations are tabulated as the number and percentage of subjects in deviation categories by as-randomized treatment group and overall for the full analysis set. Results are shown by deviation type (eligibility, subject management), category, and subcategory in the order specified in Section 9.2. Results for all relevant protocol deviation categories and subcategories are displayed, even those with 0 counts, unless specified otherwise.

A by-subject listing of relevant protocol deviations is provided for the enrolled analysis set. This includes deviation type, category, and subcategory, which are used as additional sorting variables.

6.2.4.2 Significant Protocol Deviations

A by-subject listing of significant protocol deviations is provided for the enrolled analysis set. This includes date of deviation, category, (e.g., Eligibility Criteria), subcategory (e.g., Violation of Exclusion Criteria), and description, which are used as additional sorting variables.

A Microsoft Excel file of protocol deviations is extracted from the clinical trial management system (CTMS) by Biohaven Clinical Operations. This file serves as the raw data source of protocol deviations, and classifies deviation severity as major, minor, or downgraded from protocol deviation. Significant protocol deviations are defined as those with major severity.

6.2.5 Baseline Characteristics

Baseline characteristics include (1) demographics and other relevant baseline characteristics, (2) baseline disease characteristics (i.e., migraine history, cardiac and other risk factors, prior triptan response, current triptan response, and migraine characteristics at the time of dosing), (3) medical history, and (4) prior non-study medications. These are detailed in Sections 6.2.5.1 through 6.2.5.4, respectively.

Baseline characteristics are tabulated for each of the following analysis sets as follows:

- Efficacy analysis set: Baseline characteristics (1) through (4) by as-randomized treatment group and overall to support efficacy
- Safety analysis set: Baseline characteristics (1) through (4) by as-treated treatment group and overall to support safety

- Subjects in the enrolled analysis set but not in the full analysis set: Demographics and other relevant baseline characteristics, and migraine history by overall only
- Subjects in the full analysis set but not in the efficacy analysis set: Demographics and other relevant baseline characteristics, and migraine history by as-randomized treatment group and overall.

IWRS prophylactic migraine medication use at randomization (yes, no) is tabulated by as-randomized treatment group and overall for the randomized analysis set.

Baseline for a parameter (e.g., weight) is defined according to analysis set as follows:

- Enrolled analysis set but not in the randomized analysis set: Last non-missing value
- Randomized analysis set but not in the safety analysis set: Last non-missing value at or before the IWRS randomization date
- Efficacy, safety, and outcomes research analysis sets: Last non-missing value in the pre-treatment analysis period; see Section 7.2).

“Last” is determined by the measurement date/time. Other criteria such as last entry date/time or laboratory test source may be applied to break ties on the same measurement date, as available from CRF data. See Sections 6.4.2.3, 6.4.3.1, and 6.4.4.1 for handling of ties on the same measurement date or time.

By-subject listings are provided for the enrolled analysis set for the following: demographics; medical history; migraine history; cardiac and other risk factors for subjects with any risk factor present; prior triptan response; and current triptan response. Refer to the Zavegepant Core SAP for additional details.

6.2.5.1 *Demographics and Other Relevant Baseline Characteristics*

Refer to the Zavegepant Core SAP for the table of demographics and other relevant baseline characteristics. Other relevant characteristics also include the following: IWRS prophylactic migraine medication use at randomization (yes, no); non-study stable prophylactic migraine medication use through randomization (yes, no; see Section 6.2.5.4).

6.2.5.2 *Baseline Disease Characteristics*

Refer to the Zavegepant Core SAP for tables of migraine history, cardiac and other risk factors, prior triptan response, and current triptan response.

The migraine history table also displays the number of moderate to severe migraines per month categorized as < median and \geq median, where the median is based on the efficacy analysis set (see Section 4.3).

Migraine Characteristics at the Time of Dosing

Migraine characteristics at the time of dosing include the following parameters:

- Pain intensity (none, mild, moderate, severe)
- MBS (nausea, phonophobia, photophobia) on study before dosing
- Nausea status (present, absent)
- Nausea intensity (none, mild, moderate, severe)
- Phonophobia status (present, absent)
- Phonophobia intensity (none, mild, moderate, severe)
- Photophobia status (present, absent)
- Photophobia intensity (none, mild, moderate, severe)
- Functional disability level (normal, mildly impaired, severely impaired, requires bedrest)
- Aura (yes, no) on study before dosing.

An intensity of none for a symptom (nausea, photophobia, or phonophobia) is defined as a symptom status of absent. See Section 7.5.2 for additional details.

An overall 3×3 cross-tabulation of the historical MBS (i.e., from migraine history) as rows, and the MBS reported on study before dosing as columns is presented for the efficacy analysis set with non-missing paired MBS values. The number and percentage of subjects in the following row and column categories are tabulated: nausea, phonophobia, photophobia, marginal total. In addition, the following statistics are tabulated: asymmetric lambda value and 95% CI; symmetric lambda value and 95% CI; kappa coefficient value and 95% CI; and p-value from the chi-square test.

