- a) History of drug or other allergy which, in the opinion of the Investigator, makes the subject unsuitable for participation in the study.
- 4) Sex and Reproductive Status
- a) Females of child-bearing potential who are unwilling or unable to use an acceptable contraceptive method or abstinence to avoid pregnancy for the entire study period and for 90 days after the study.
-

- b) Women who are pregnant, lactating or breastfeeding.
 - c) Women with a positive pregnancy test.
- 5) ECG and Laboratory Test Findings
- a) Estimated glomerular filtration rate (eGFR) according to the re-expressed abbreviated (4-variable) Modification of Diet in Renal Disease (MDRD) Study equation ≤ 40 ml/min/1.73m².
 - b) Corrected QT interval > 470 msec (QTc by method of Frederica), at Screening.
 - c) Left Bundle Branch block.
 - d) Right Bundle Branch Block with a QRS duration ≥ 150 msec.
 - e) Intraventricular Conduction Defect with a QRS duration ≥ 150 msec.
 - f) Serum bilirubin (Total, Direct or Indirect) > 1.5 x ULN are excluded. However, abnormal values of between 1-1.5x ULN may be considered but must be repeated once for confirmation during the screening period. Repeat results **must** be the same or lower than the first lab result in order to remain eligible for the study. Subjects must be excluded if repeat is > 1.5 x ULN.
 - g) Neutrophil count $\leq 1000/\mu\text{L}$ (or equivalent).
 - h) AST (SGOT) or ALT (SGPT) >1.5 x ULN are excluded. However, abnormal values of between 1-1.5x ULN may be considered but must be repeated once for confirmation during the screening period. Repeat results **must** be the same or lower than the first lab result in order to remain eligible for the study. Subjects must be excluded if repeat is >1.5 x ULN.
- 6) Other Exclusion Criteria:
- a) Prisoners or subjects who are involuntarily incarcerated.
 - b) Subjects who are compulsorily detained for treatment of either a psychiatric or physical (e.g., infectious disease) illness.
 - c) Score of > 0 on the Sheehan Suicidality Tracking Scale for the period of 30 days prior to Screening and during the study.
 - d) Participation in clinical trial with non-biological investigational agents or investigational interventional treatments (last study visit occurring) within the 30 days prior to Baseline Visit.
-

- e) Subjects who have previously participated in any BHV-3500 study (re-screens for this study, (BHV3500-301), may be considered, as described in inclusion criteria 6b above).

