6.4.2 Laboratory Tests

Laboratory tests are analyzed using results from the external central laboratory CCI [REDACTED] which identifies expired kits, and from local laboratory tests reported on CRFs. The central laboratory reports both laboratory collection date and time, whereas CRFs capture only laboratory collection date.

Clinically significant laboratory abnormalities are identified as grade 3 to 4 laboratory test results. Refer to the Zavegepant Core SAP for laboratory tests of clinical interest for analyses, including identification of those with toxicity grades.

The following by-subject laboratory test listings are provided for the enrolled analysis set:

- Select laboratory test groups: hematology (both SI and US units)*; serum chemistry (both SI and US units)*; urinalysis (US units only)*; pregnancy (US units only)*; endocrinology, serology, drug screen, and miscellaneous laboratory tests (US units only). The pregnancy listing identifies positive pregnancy tests, which are defined as serum or urine pregnancy tests with either (a) “positive” character value, or (b) numeric value ≥ 25 U/L.
- Liver function test (LFT) values and ratios to ULN (i.e., alanine aminotransferase [ALT], aspartate aminotransferase [AST], total bilirubin [TBL], and alkaline phosphatase [ALP]) for both US and SI units*. The listing displays all LFT results over time for subjects with select LFT elevations (ALT or AST $> 3x$ ULN; ALP or TBL $> 2x$ ULN) at any time point.

- Creatine kinase (CK) elevation questionnaire.

Listings display toxicity grades and identify expired kits from the central laboratory, if applicable, and those marked with “*” display COVID-19 visit impact code for visits impacted by COVID-19 (see Section 9.1.5.2). Refer to the Zavegepant Core SAP for listing contents.

6.4.2.1 *Laboratory Test Abnormalities*

On-treatment laboratory test abnormalities are tabulated as the number and percentage of subjects in the safety analysis set in the following frequency tables:

- Worst (highest) on-treatment laboratory test abnormality for each graded laboratory test.
- Laboratory test toxicity grade shift from baseline to the worst on-treatment toxicity grade for each graded laboratory test.
- Laboratory test low/normal/high shifts from baseline to any abnormal on-treatment value for each laboratory test with normal ranges.

Refer to the Zavegepant Core SAP for toxicity grade categories and additional details.

6.4.2.2 *Liver Function Test Elevations*

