Refer to the Zavegepant Core SAP for additional details.

LFT Elevations: Cumulative, Mutually Exclusive, and Composite

The number and percentage of subjects with LFT elevations are tabulated separately for each analysis period (pre-treatment, on-treatment) for the safety analysis set. LFT elevations are based on fold changes above ULN.

LFT ULN Shifts from Baseline to Worst Elevation

LFT ULN shifts from baseline to the worst (highest) on-treatment LFT elevation are tabulated as the number and percentage of subjects in the safety analysis set in pre-specified elevation categories.

eDISH Scatter Plot

An evaluation of drug-induced serious hepatotoxicity (eDISH) scatter plot displays the maximum TBL ratio of value to ULN on the y-axis versus the maximum ALT ratio of value to ULN on the x-axis by treatment group, where both maxima are on treatment but not necessarily concurrent.

6.4.2.3 *Laboratory Test Changes from Baseline*

Values and changes from baseline in laboratory tests are tabulated as continuous variables at baseline and the end of treatment visit.

If a subject has multiple values in the end of treatment analysis visit window, then a single value is selected using the following hierarchy as available:

- Non-missing viable value collected last. If there are multiple viable values on the same date, then the following hierarchy is used as available:
 - Last central laboratory test value collected timewise with the last accession identifier.
 - Last local laboratory test value entered.

Viable laboratory test values are defined as those from (1) kits from the central laboratory that are not expired (see Section 6.4.2), or (2) local laboratory tests reported on CRFs.

- Non-missing value from an expired kit from the central laboratory collected last. If there are multiple values on the same date, then the value with the last accession identifier is used.

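### Laboratory baseline is chosen by date alone, so a later expired-kit value can displace an earlier viable one that SAP 6.4.2.3 would prefer at end of treatment

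*SAP*

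**What the plan says.** **Baseline.** For the safety set, SAP 6.2.5 gives the rule "Efficacy, safety, and outcomes research analysis sets: Last non-missing value in the pre-treatment analysis period". Which value is last "is determined by the measurement date/time". Other criteria serve only to separate values on the same measurement date, and the link to the laboratory section is equally limited: "See Sections 6.4.2.3, 6.4.3.1, and 6.4.4.1 for handling of ties on the same measurement date or time". Kit expiry is not mentioned. Under SAP 7.2 the pre-treatment period runs up to and including the start of study drug.

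**End of treatment.** SAP 6.4.2.3 begins: "If a subject has multiple values in the end of treatment analysis visit window, then a single value is selected using the following hierarchy". Viable values come first: "Viable laboratory test values are defined as those from (1) kits from the central laboratory that are not expired", together with local laboratory results entered on CRFs. Second in rank, used only when there is no viable value, is: "Non-missing value from an expired kit from the central laboratory collected last". SAP 6.4 also describes this laboratory algorithm as one for the end of treatment window.

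**Where baseline is used.** It enters the change tables (SAP 6.4.2.3), the liver test shift table (SAP 6.4.2.2) and the shift tables of SAP 6.4.2.1, such as: "Laboratory test toxicity grade shift from baseline to the worst on-treatment toxicity grade for each graded laboratory test".

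**Why a subject may have several pre-treatment values.** Protocol Table 1 schedules safety laboratory tests at screening and end of treatment only. However, under Protocol 5.3 (criteria 5f and 5h), bilirubin, AST or ALT between 1 and 1.5x ULN "must be repeated once for confirmation during the screening period". Protocol 6.3.4 also calls for repeats of clinically significant abnormal results.

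**The concern.** A change from baseline subtracts one selected value from another. In SAP 6.4.2.3 the plan sets a quality standard, under which an expired-kit result gives way to a viable one. It applies that standard explicitly to the end of treatment value but not to the baseline. Other safety parameters use the last non-missing value at both ends; the laboratory tests do not.

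The situation can arise for the liver tests because a second screening draw is mandatory for borderline values. Protocol 5.3 keeps such a subject eligible only if the repeat is no higher than the first result. For that mandatory repeat, taking the later value as baseline can therefore only lower the reference or leave it unchanged. If an expired-kit repeat is inaccurate, the effect on the table is towards an apparent rise on treatment. What is at stake is the liver change and shift tables for the subjects affected.

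**Working it through.** The plan states no figure on this point, so there is none to reproduce. The check applies both rules to the same sets of pre-treatment values and compares the choice.

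**Inputs**
- Rule A (SAP 6.2.5): take the latest measurement date; send values sharing that date to SAP 6.4.2.3.
- Rule B (SAP 6.4.2.3, applied in full to the pre-treatment period): take the last viable value; use an expired-kit value only if there is no viable one.
- The days below are assumed, for illustration, relative to dosing.

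| Pre-treatment values | Rule A selects | Rule B selects |
|---|---|---|
| (a) Viable day -20, expired-kit repeat day -5 | Expired | Viable |
| (b) Expired-kit day -20, viable redraw day -5 | Viable | Viable |
| (c) Same day, viable first, expired-kit later | Viable if the tie reference carries the viable-first order; expired if clock time alone decides | Viable |
| (d) Expired-kit value only | Expired | Expired |
| (e) Viable value only | Viable | Viable |

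The rules differ in (a), and the text is ambiguous in (c). In the other three cases they agree.

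**Size for one affected subject (assumed values)**

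Reported change = end of treatment value - selected baseline.
- Viable ALT at first screening draw: 1.4x ULN. Expired-kit repeat: 0.9x ULN. Viable end of treatment value: 1.4x ULN.
- Rule A: 1.4 - 0.9 = +0.5x ULN, a shift from normal to above ULN.
- Rule B: 1.4 - 1.4 = 0, above ULN at both ends.

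The two results differ by the gap between the pre-treatment values. As the repeat runs from 0.9 to 1.4x ULN, that gap falls from 1.4 - 0.9 = 0.5 to 1.4 - 1.4 = 0. For a mandatory repeat the first value is at most 1.5x ULN and the repeat is no higher, so the gap cannot exceed 1.5x ULN minus the repeat value.

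**Outputs that use baseline**
- Affected: change tables; toxicity-grade and low/normal/high shift tables; liver test shift table.
- Not affected: worst on-treatment grade counts and the eDISH plot, which use on-treatment values; liver elevation counts, which are tabulated within each analysis period; all efficacy analyses.

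**The case against.** The case for leaving the text alone has several parts.

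1. **Same-date ties may already be covered.** SAP 6.2.5 points to SAP 6.4.2.3 for ties, and the revision history shows that this reference and the viability definition arrived together in SAP version 5.0. A reader might infer that viable-first never applies to baseline. The documents do not support that; same-date values can reasonably be read as covered. This stands, and it leaves only different-date values clearly outside the rule.
2. **The configuration is uncommon.** It needs two pre-treatment draws on different dates, with the later from an expired kit and the earlier viable. A redraw made because a kit had expired would normally be later and viable, and the present rule already selects it. This stands. A reader might conclude that laboratory changes and shifts are unreliable in general; nothing in the documents supports that.
3. **An expired-kit value need not be wrong.** The SAP uses such values when nothing else exists, and a lower confirmatory repeat may be genuine. This stands. In the example, 0 is the viable-to-viable change and not a known true change. The argument is one of consistency with the SAP's own ranking.
4. **The worst-value outputs are a separate matter.** A reader might see a contradiction if a subject has a grade 3-4 result in the worst-grade table and a normal end of treatment value. These are different summaries, and they diverge whenever an abnormal result resolves on repeat. Keeping every value in a worst-case safety table is conservative, and SAP 6.4.2 has listings identify expired kits. This stands.
5. **The Core SAP is not available.** SAP 6.4.2.1 and 6.4.2.2 defer further details to it, so it might hold a relevant rule. That cannot be checked. SAP 6.2.5 and 6.4.2.3 nevertheless state their selection rules directly, and neither refers to it for the viability of baseline values.

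**Conclusion.** The point holds in a narrow form. For pre-treatment laboratory values on different dates, SAP 6.2.5 lets a later expired-kit value displace an earlier viable one, whereas SAP 6.4.2.3 makes the reverse choice at end of treatment. The rules are different rather than opposite: both take the last value, but only one puts viability ahead of date.

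The number of subjects cannot be computed, because neither document counts expired kits or repeat draws; it is probably small. For an affected subject, the whole difference between the two pre-treatment values passes into the reported change. The consequence is confined to descriptive safety tables. This is an inexpensive improvement to the plan and not a threat to its conclusions. It assumes that the Core SAP contains no overriding baseline rule.

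**What to change.** In SAP 6.2.5, add a sentence on laboratory tests along these lines: *baseline is the last viable value, as defined in Section 6.4.2.3, over the whole pre-treatment period; a value from an expired central kit is used only if no viable value exists; the same order applies to values on the same date.* State that this baseline is used in the shift tables of SAP 6.4.2.1 and 6.4.2.2 and in the change tables of SAP 6.4.2.3. Make the change before unblinding, so that the choice of baseline is not made after the fact.

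The cost is SAP wording and re-use of a selection routine already needed for end of treatment. The downside is an earlier baseline date for a few subjects. A footnote marking worst on-treatment values that come from expired kits is optional; those values should stay in the tables.
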